Goal

The aim of this study is to evaluate the effect of breastfeeding education given by teach-back method on breastfeeding success.

Hypotheses

H0: Breastfeeding training given by Teach-Back method has no effect on breastfeeding success.

H1: Breastfeeding training given by Teach-Back method has an impact on breastfeeding success.

Methods

Study design

This study, which has a randomized controlled experimental research design, was conducted between 15 January and 15 December 2018. The sample of the study was divided into two groups by randomization. Breastfeeding success levels were compared by providing breastfeeding education and counseling service based on the teach-back method to one group of mothers (intervention group), and standard breastfeeding education and counseling service to another group (control group). Opinions were received from five academicians working in the field of Midwifery, Obstetrics and Gynecology Nursing, who have researches on breastfeeding. Recommendations from the CONSORT group (Consolidated Standards of Reporting Trials) were followed in this study (Schulz et al., 2010).

Sample and setting

Women who live in a city center where is in Turkey's Central Anatolia and have a vaginal birth, literate, primipar, in term and healthy. Those excluded from the inclusion criteria were excluded from the study.

The study was carried out in the City Hospital, where the number of births in the city center was the highest in a year, and in the Family Health Centers where maternal and infant follow-ups were performed. The first stage of the study, which was the stage of meeting women, was done in the maternity unit and postpartum service of the City Hospital, since women who gave vaginal births were

discharged after 24 hours if no problem developed. The second stage of the study was carried out in Family Health Centers where women are affiliated.

Sample size calculation

The universe of the study was composed of women who had vaginal births in the City Hospital between years 2017-2018. According to the hospital records, in the first 6 months of 2017, the total number of births was determined as 1455, and the number of non-invasive vaginal births was 590. The minimum number of individuals to be included in the sample of the study was calculated using the "G-power 3.1.3" program based on the data of the study titled "The effect of antenatal training based on strengthening breastfeeding self-efficacy perception and breastfeeding success" (Tokat Aluş & Okuş, 2013). Considering the sample size of the research and the mean scores obtained from this study, the LACTH scale scores will increase 0.5 points after the application, with the pre-acceptance of the clinical effect to be 5% of Alpha error and 80% of the power of the study (Effect Size: 0.70) and it was determined that there should be at least 31 people in each group (Tokat Aluş & Okumuş, 2013). A total of 80 women, 40 studies and 40 control groups, were included in the sample. Women who had vaginal births meeting the inclusion criteria were selected by simple random randomization into the intervention and control group.

Randomization

Considering the inclusion and exclusion criteria, women were divided into simple randomization intervention and control groups. In the randomization of the sample, "Research Randomizer" was used. The randomization process was created by a neutral researcher who was not involved in the study. The women were not informed about the groups they were in. Single blind was provided in the study by knowing which group they would be in by the researcher.

Intervention

The study was carried out in two stages. In the first stage, in the first 24 hours at the postpartum period, the researcher interviewed the women who gave birth in the postpartum care units of the hospital and

determined the women who volunteered to participate in the research and that comply with the inclusion criteria and received their informed consent. Women were divided into randomized intervention or control groups. When the postpartum mother and baby's health condition was stable, "Personal Information Form" was applied to mothers. After the women were informed about the appointments and dates at the Family Health Centers where the second phase of the research will be carried out, the home and mobile numbers of the researcher were given to them in writing. The meeting ended with the mothers about the time and place of the next visits.

In the second stage of the study, three interviews were held with the mothers on the dates determined in the first stage of the study. In these interviews, the mothers in the intervention group were asked by the researchers about the needs of breastfeeding by using the relevant literature (Ekşioğlu, 2016; Hannula, Kaunonen, & Tarkka, 2008; Maleki-Saghooni et al., 2017; RNAO, 2018). Training and counseling based on the Teach-back method was given in the Family Health Centers (FHC) where they are registered. Turkey Ministry of Health's Postpartum Care Management Guidelines (2014) was carried out with mothers enrolled in FHC in the control group, on the basis of three interviews. In these interviews, standard training and counseling services were offered on breastfeeding. While providing standard training and counseling services, "Breastfeeding Training Guide" used in the intervention group was taken as the basis. The method of straight expression, which is mostly used by breastfeeding counseling provider healthcare professionals in Turkey, was used. In standard education, whether the learning is achieved is tested by closed-ended, "yes-no" questions structured as "Did you understand?". After, it is controlled by asking whether there are any questions about the subject. The trainings of both groups were given individually in a separate room at FHCs.

Measurements and data collection

Based on the literature information (Faridvand, Mirghafourvand, Malakouti, & Mohammad-Alizadeh-Charandabi, 2017; Jeon & Hwang, 2013; Maleki-Saghooni et al., 2017; Tarrant, Younger, Sheridan-Pereira, & Kearney, 2011) an information form was developed by researchers. The form consisted of a total of 28 questions, including the socio-demographic and personal characteristics of women in the intervention and control group (16 questions), questions related to birth, postpartum period and

breastfeeding (12 questions). “LATCH Breastfeeding Diagnosis and Evaluation Scale” and “Postpartum Breastfeeding Self-Efficacy Scale Short Form” were used to evaluate breastfeeding success. The Breastfeeding Training Guide used in the education of mothers was created by scanning the literature on the subject (Aittasalo et al., 2006; Badaczewski et al., 2017; Farris, 2015; Tamura-Lis, 2013; Tokat, Okumuş, & Dennis, 2010) and in line with the recommendations of 5 academics specialized in Obstetrics and Gynecology Nursing. In order to evaluate the performance of the researcher using the Teach-back method, the “Teach-Back Method Observation Tool” recommended by the developers of this method was used.

Data Collection

In the first stage of the study, women were interviewed in postpartum care units, and when the health condition of the mother and baby was stable, the Personal Information Form was applied to the mothers.

In the second stage of the study, 3 interviews were conducted with the mothers in the intervention and control groups during the 2-5th postpartum days, 13-17th days and 30-42nd days. In the first meeting of the second phase, the pre-education Breastfeeding Diagnostic Tool LATCH and Postpartum Breastfeeding Self-Efficacy Scale were applied to the mothers in the intervention and control groups. Breastfeeding training and counseling services were provided to the mothers in the intervention group, based on the teach-back method, and those in the control group using the standard breastfeeding training technique. This interview lasted an average of 1 hour.

In the second meeting of the second stage, which was held between the 13th and 17th days of birth, the pre-education Breastfeeding Diagnostic Tool LATCH and Postpartum Breastfeeding Self-Efficacy Scale were applied to the mothers in the intervention and control groups. Breastfeeding training and counseling services were provided to the mothers in the intervention group, based on the teach-back method, and those in the control group using the standard breastfeeding training technique. This interview took an average of 40-45 minutes.

In the third meeting of the second stage, which was held between the 30-42th days of birth, the pre-education Breastfeeding Diagnostic Tool LATCH and Postpartum Breastfeeding Self-Efficacy Scale

were applied to the mothers in the intervention and control groups. Breastfeeding training and counseling services were provided to the mothers in the intervention group, based on the teach-back method, and those in the control group using the standard breastfeeding training technique. This interview took an average of 40-45 minutes.

Statistical analysis

The data of the study were evaluated on computer by using Statistical Package for Social Sciences (SPSS) (22.0) program. In the evaluation of the data;

- The distribution of the data was evaluated with the Kolmogorov-Smirnov test. Since it showed a normal distribution, parametric tests were used in the analyzes.
- The homogeneity of the groups was assessed by chi-square test in categorical variables, Mann Whitney U in numerical variables, or T test in independent groups.
- In the intervention and control groups, “Multifaceted Variance Analysis in Repeated Measurements” was performed in comparing the LATCH breastfeeding diagnosis and evaluation scale and the breastfeeding self-efficacy scale according to the group, time and group * time interaction.
- In the advanced analysis of the difference between the LATCH, breastfeeding diagnostic and evaluation scale, and breastfeeding self-efficacy scale averages in the intervention and control groups, “One-Way Variance Analysis in Repetitive Measurements” to compare the mean scores of the groups within themselves, “Bonferroni Correction Dependent Groups T-Test” to compare the measurements with each other.

Ethical consideration

Before starting the research, permission was obtained from the Konya Chamber of Commerce, Karatay University Rectorate Medical Faculty Non-Device Research Ethics Committee (Date: 26.12.2017 and Number no: 006). Institution permissions were obtained from Yozgat City Hospital (Date: 05.02.2018 and Number: 78.535.428-799) and Provincial Health Directorate Family Health Unit (Date: 11.06.2018 and Number: 92.198.657-060.11.01).

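### The stated 80% power (effect size 0.70, 31 per group) is not tied to any test of LATCH that the plan makes

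*SAP*

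**What the plan says.** **Sample size calculation.** The effect is taken from a cited study of antenatal training and worded as "the LACTH scale scores will increase 0.5 points after the application". The other inputs are 5% alpha, "80% of the power of the study" and "Effect Size: 0.70". The result is that "there should be at least 31 people in each group"; 40 per arm were included. The section gives no statistical test, sidedness, SD, time point or difference between arms.

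**Intervention and Data Collection.** Both arms receive individual training at three meetings (days 2-5, 13-17 and 30-42). For the control sessions the training guide "used in the intervention group was taken as the basis". LATCH is recorded before the education at each meeting, so the first value precedes all training.

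**Statistical analysis.** LATCH is compared by repeated-measures analysis of variance "according to the group, time and group * time interaction". The follow-up tests are a one-way repeated-measures analysis within each arm and Bonferroni-corrected paired t-tests. Independent-groups tests appear only for checking that the groups are homogeneous.

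**The concern.** A power figure means something only for a named test of a named difference. Here there are two gaps.

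- **The test.** A sample size stated per group, at a standardised effect of 0.70, looks like one comparison of two means. The plan makes no such comparison of LATCH. Its between-arm tests are the group term, which averages in a visit at which randomised arms should not differ, and the group-by-time term, which has 2 degrees of freedom. The plan does not say which of the two decides H1.
- **The effect.** The 0.5 points are worded as an increase, and no between-arm difference appears anywhere. If 0.5 is a rise within the trained arm, it overstates the gap between arms by whatever the control arm also gains, and that arm is trained from the same guide.

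At stake is how a null result is read. A reader would set it against 80% power, a figure that was worked out for neither F-test.

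**Working it through.** **Inputs from the SAP:** effect size 0.70; raw effect 0.5 LATCH points; alpha 5%; power 80%; 31 per group required; 40 per arm included; three LATCH measurements, the first before training.

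**Assumptions, because the SAP is silent:** two-sided test; equal correlation ρ between any two visits, 0.3 to 0.7; equal variances; arms equal at the first meeting; true gap of 0.70 SD at the third meeting.

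**1. Reproducing 31 per group**

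- Implied SD = 0.5 / 0.70 = 0.71 points.
- Two independent means, normal approximation: n = 2 × ((1.960 + 0.842) / 0.70)² = 32.04, so 33 per group.
- Exact two-sided t-test: 33.02, so 34 per group. Power at 31 is 77.4%; at 40 it is 87.1%.
- One-sided Mann-Whitney with the minimum relative efficiency 0.864: 25.94 / 0.864 = 30.02, so 31 per group.
- Paired before-after t-test at 0.70: 18.03, so 19 women.
- Repeated-measures F-tests at f = 0.35 and ρ = 0.5: 23 per arm for group and 8 for interaction. The group term reaches 31 only at ρ near 0.9.

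The stated 31 therefore sits close to a two-group comparison and far from a paired one. It matches the repeated-measures tests only at a correlation that is nowhere stated.

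**2. Power of the planned tests at 40 per arm**

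Let δ be the arm gap in SD units at each visit, and n = 40. The noncentrality parameters are:

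- Group: λ = (n/2) × 3 × mean(δ)² / (1 + 2ρ), on 1 and 78 df.
- Interaction: λ = (n/2) × Σ(δ − mean δ)² / (1 − ρ), on 2 and 156 df.
- Third-meeting difference adjusted for the first: λ = (n/2) × 0.70² / (1 − ρ²), on 1 and 77 df.

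Example with gaps 0, 0.35, 0.70 and ρ = 0.5:

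- group: λ = 20 × 3 × 0.1225 / 2 = 3.675, power 47%;
- interaction: λ = 20 × 0.245 / 0.5 = 9.8, power 80%;
- adjusted difference: λ = 20 × 0.49 / 0.75 = 13.07, power 95%.

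| Test, 40 per arm | ρ = 0.3 | ρ = 0.5 | ρ = 0.7 |
|---|---|---|---|
| Group, gap grows linearly | 56% | 47% | 41% |
| Group, gap complete by second meeting | 81% | 71% | 64% |
| Interaction, gap grows linearly | 65% | 80% | 96% |
| Interaction, gap complete by second meeting | 78% | 90% | 99% |
| Third-meeting difference, baseline-adjusted | 90% | 95% | 99% |

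**3. If 0.5 is a within-arm rise and controls also gain**

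The quarter and half gains below are illustrations; the SAP gives no figure. Two-group t-test at 40 per arm:

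- controls gain nothing: gap 0.5, effect size 0.70, power 87%;
- controls gain a quarter of 0.5: gap 0.375, effect size 0.525, power 64%;
- controls gain half of 0.5: gap 0.25, effect size 0.35, power 34%.

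**The case against.** - **The sample-size test is inferred.** True. The SAP names none, and an exact two-sided t-test needs 34, not 31. The inference rests on the per-group wording and on the arithmetic above. The shortfall of 31 against 34 does no harm, because 40 per arm were included.
- **The 0.5 may already be a net difference.** A reader might infer that a before-to-after rise was mistakenly used as the gap between arms. The document does not establish this. The sentence is ambiguous, the cited study is not at hand, and the phrase may mean the gain due to the intervention. In that case control improvement is already allowed for, and only the wording needs repair. What stands is that no between-arm difference is stated.
- **Sizing on two means and analysing by repeated measures is common and can be conservative.** Also true: the interaction tests directly whether the course of LATCH differs between arms, and at ρ of 0.5 or more it has about 80% power or better at 40 per arm for the full 0.70 SD gap. But whether the simplification is conservative depends on which F-test decides H1, on the correlation and on when the gap opens. The SAP fixes none of these.
- **The SAP is written in the past tense, for a study run from January to December 2018.** A new deciding test may therefore be a post hoc choice. This stands, and the fix must carry that label if outcome data have been seen.

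**Conclusion.** The point holds in a limited form: the 80% is the power of no test of LATCH that the plan makes, and the effect behind it is not stated as a difference between arms. The size of the mismatch depends on the assumptions listed (0.70 SD gap at the third meeting, equal visit correlations of 0.3 to 0.7, arms equal before training). Under them the group test falls below 80% in nearly every setting, while the interaction runs from below 80% to well above it.

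A reader might conclude that the trial is underpowered. The documents do not support that: 40 per arm exceeds the stated minimum, and several settings give the interaction ample power. The low group-test figures would matter only if that test decided H1, which the SAP does not say.

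**What to change.** No further women or measurements are needed.

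1. State the planning effect as a between-arm difference of 0.5 LATCH points at the third meeting, with the implied SD of 0.71. If the cited study's 0.5 was a within-arm rise, say so.
2. Make that third-meeting difference, adjusted for first-meeting LATCH, the test that decides H1 and to which the power refers. Label it post hoc if outcome data have already been seen.
3. Replace the single 80% with the power at 40 per arm for differences of 0.5, 0.375 and 0.25 points: 87%, 64% and 34% before any gain from baseline adjustment.

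**Cost:** a change of SAP text and of the deciding analysis, using data already collected. The repeated-measures F-tests become supportive, and the stated power looks less favourable if controls also improve.

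### The stated minimum of 31 women per group does not follow from effect size 0.70, 5% alpha and 80% power under a two-group t-test

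*SAP*

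**What the plan says.** The Sample size calculation section of the SAP reports a G-power 3.1.3 calculation based on the mean scores of an earlier study of antenatal breastfeeding training. Its clinical premise is that "the LACTH scale scores will increase 0.5 points after the application". The error rates are "5% of Alpha error and 80% of the power of the study", and the result is given as "Effect Size: 0.70) and it was determined that there should be at least 31 people in each group". The section then reports the number actually included: "A total of 80 women, 40 studies and 40 control groups, were included in the sample".

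The section does not name the statistical test, the number of sides, the type of effect size or a standard deviation. Two other places bear on the reading:

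- The Hypotheses section gives a non-directional alternative: "H1: Breastfeeding training given by Teach-Back method has an impact on breastfeeding success".
- The Statistical analysis section says parametric tests were used. It assigns LATCH to a repeated-measures analysis of variance by group, time and their interaction, which "was performed in comparing the LATCH breastfeeding diagnosis and evaluation scale" and the self-efficacy scale.

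**The concern.** The section gives what a reader needs for the simplest two-group calculation: a standardised effect, an alpha, a power and a number per group. The effect is also described as a difference in mean score between two randomised groups, so an independent-groups t-test is the natural first check. Under that check the inputs and the output disagree.

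The figure of 31 is the only adequacy threshold in the document. If losses had brought the analysed groups down to 31, a reader would take 80% power as preserved, whereas the stated inputs under a two-sided t-test give less. The sample size statement also cannot be verified as written.

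**Working it through.** **Inputs from the Sample size calculation section.** Effect size 0.70, taken as Cohen's d because the type is not named; alpha 0.05; power 0.80; equal groups, as in the 40 and 40 included. The number of sides is not stated. The non-directional hypothesis points to two-sided, but both are shown.

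**Formula (exact t-test, n per group).** Degrees of freedom 2n − 2; noncentrality δ = d·√(n/2). Power is the probability that a noncentral t variable with noncentrality δ exceeds the critical value (in either tail if two-sided).

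**The plan's own figure, n = 31.** δ = 0.70 × √15.5 = 2.756, with 60 degrees of freedom.

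- Two-sided: critical value 2.000, power 77.4%, which is 2.6 points below 80%.
- One-sided: critical value 1.671, power 86.0%, which is 6.0 points above 80%.

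**Minimum n for 80% power at d = 0.70.**

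| n per group | Two-sided power | One-sided power |
|---|---|---|
| 25 | 67.9% | 78.7% |
| 26 | 69.7% | 80.1% |
| 31 | 77.4% | 86.0% |
| 33 | 79.97% | 87.9% |
| 34 | 81.2% | 88.7% |
| 40 | 87.1% | 92.8% |

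The two-sided minimum is 34 (33.02 before rounding up). The one-sided minimum is 26 (25.94 before rounding up). The stated 31 is 3 too few for one and 5 more than needed for the other, so the choice of sides does not explain it.

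**Normal approximation.** n = 2(z₁₋α/₂ + z₀.₈₀)²/d² = 2 × (1.960 + 0.842)²/0.49 = 32.04, so 33 two-sided, with 78.7% power at 31. One-sided: 2 × (1.645 + 0.842)²/0.49 = 25.23, so 26. Neither gives 31.

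**Rounding of the effect size.** The two-sided minimum equals 31 only for d from 0.7232 to 0.7356. Values that round to 0.70 at two decimals do not reach this: d = 0.695 gives 34 and d = 0.705 gives 33.

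**Settings that do return 31 at an effect size of 0.70.**

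- One-sided t-test at 85% power: 30.04, so 31. This contradicts the stated 80%.
- Mann-Whitney test, dividing the t-test n by the relative efficiency. Two-sided with a logistic parent distribution (efficiency π²/9 = 1.097): 33.02/1.097 = 30.1, so 31. One-sided at the minimum efficiency of 0.864: 25.94/0.864 = 30.02, so 31. With a normal parent the results are 35 two-sided and 28 one-sided.
- Between-group test in a repeated-measures design with m = 3 measurements, N = 62 and f = d/2 = 0.35 (an assumption). The noncentrality is λ = f²·N·m/(1 + (m − 1)ρ) = 0.1225 × 62 × 3/(1 + 2ρ) = 22.785/(1 + 2ρ), on 1 and 60 degrees of freedom. The minimum is 31 when the correlation ρ lies between about 0.858 and 0.905.

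**What 31 gives for that repeated-measures between-group test.** With f = 0.35:

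| ρ | λ | Power at 31 per group |
|---|---|---|
| 0.5 | 11.39 | 91.3% |
| 0.7 | 9.49 | 85.8% |
| 0.9 | 8.14 | 80.1% |

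Power stays at or above 80% for any correlation from 0 up to about 0.905.

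**The case against.** The strongest reply is that the t-test is a reviewer's assumption. The plan names no test for the calculation, and its LATCH comparison is a repeated-measures analysis of variance. The Statistical analysis section mentions an independent-groups t-test only for checking that the groups are comparable. Some settings reach 31 without altering any stated number: the two Mann-Whitney variants, and the repeated-measures test with a high correlation. On this view the document shows an incomplete description and not a proven arithmetic error. The gap is also narrow: exact two-sided power at 33 is 79.97%, and an effect size of 0.723 to 0.736 is still 0.7 to one decimal. Finally, the study is reported as already conducted with 40 per group, so the correction changes nothing in recruitment.

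Much of this stands. It cannot be said that the sample size is the faulty figure, and nothing here shows an underpowered trial. But each route to 31 needs an input the plan does not give: a parent distribution or efficiency, or an f with a correlation. The Mann-Whitney routes also sit badly with a plan that says it used parametric tests. These routes show that 31 may have an undisclosed origin; they do not show that it follows from what is written. Rounding to one decimal is possible, but the plan prints 0.70 to two.

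**Conclusion.** The concern holds, as a minor correction to a stated figure. Under a two-group t-test with d = 0.70, 5% alpha and 80% power, the minimum is 34 per group two-sided or 26 one-sided, not 31. The conclusion rests on reading 0.70 as Cohen's d and on the independent t-test as the benchmark. The document does not settle whether the n, the effect size, the power or the test setting is at fault.

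The 40 per group included exceed 34, and two-sided power stays above 80% down to 34 analysed per group. For the repeated-measures between-group test no shortfall is shown, conditional on the assumed f of 0.35 and a correlation no higher than about 0.905. Confidence is medium because the setting used in G-power is not visible.

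**What to change.** Make the effect size, power, test and number per group agree in the Sample size calculation section, by one of three routes:

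- restate the minimum as 34 per group, naming a two-sided independent t-test with d = 0.70, 5% alpha and 80% power;
- correct the effect size or the power to the value actually entered; or
- name the G-power test and settings that returned 31, including the number of sides and, where they apply, the parent distribution or the f, number of measurements and correlation.

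The third route is the right one if the calculation was made for the repeated-measures analysis, since the first would write a t-test into a calculation that did not use it. In addition, state that the 40 per group included give about 87% power at d = 0.70 (two-sided t-test) before losses.

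The cost is a change of SAP wording only.

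### The single hypothesis on breastfeeding success is tested on two scales of equal standing, and no rule or correction across the scales says when H0 is rejected

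*SAP*

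**What the plan says.** - **Hypotheses.** There is one pair. The alternative reads "H1: Breastfeeding training given by Teach-Back method has an impact on breastfeeding success". It names no scale, visit or model term.
- **Measurements and data collection.** LATCH and the short-form self-efficacy scale "were used to evaluate breastfeeding success". Neither is called primary or secondary.
- **Sample size calculation.** This uses one scale only: "the LACTH scale scores will increase 0.5 points after the application" (taken here to mean LATCH). The inputs are a 5% alpha, "80% of the power of the study" and "Effect Size: 0.70". The result is at least 31 women per group, and 40 per group were included.
- **Statistical analysis.** Both scales are compared by repeated-measures ANOVA "according to the group, time and group * time interaction". Follow-up consists of a one-way repeated-measures ANOVA within each group and Bonferroni-corrected paired t-tests between measurements. This section gives no significance level.

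**The concern.** The hypothesis concerns one concept, but two scales measure it and the analysis section treats them alike. The SAP does not say whether H0 falls on LATCH, on self-efficacy, on either or only on both. The one multiplicity correction applies to paired comparisons between visits. Those do not compare the arms, so they do not protect the test of H1.

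Two things are at stake. If either scale may carry the claim, the error rate for the trial's only hypothesis exceeds the level used to size it. If the scales disagree, whether H1 was supported can be settled after the results are known.

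**Working it through.** **Inputs from the SAP:** alpha 5%, power 80%, effect size 0.70, 31 per group required, 40 per group included, two scales, three measurements.

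**Assumptions:** two-sided tests, 5% applied to each scale, H0 rejected if either scale is significant, between-scale correlation r from 0 to 0.9. The SAP gives none of these.

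**1. The plan's own figure.** For a two-sample comparison of means, n per group = 2(1.96 + 0.8416)² / 0.70² = 2 × 7.849 / 0.49 = 32.04, so 33. The exact t calculation gives 34. The stated 31 has a power of 78.7% (normal) or 77.4% (exact t), so it is reproduced approximately. The calculation has room for one outcome at the full 5% and does not refer to a second.

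**2. One test per scale, either suffices.** If the scales are independent, the rate is 1 − (1 − 0.05)² = 0.0975. The upper bound is 0.05 + 0.05 = 0.10. For correlated tests it is 1 − P(|Z₁| < 1.96 and |Z₂| < 1.96), with (Z₁, Z₂) bivariate normal with correlation r.

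The group-by-time test has 2 degrees of freedom and is not a z-test. The result was therefore checked by simulating the F-tests with no true effect: 40 per arm, three visits, an assumed visit correlation of 0.5 and 20,000 runs. The last row also counts the group main effect on each scale, which makes four tests.

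| Between-scale correlation | 0 | 0.3 | 0.5 | 0.7 | 0.8 | 0.9 |
|---|---|---|---|---|---|---|
| Bivariate normal, two tests (%) | 9.75 | 9.5 | 9.1 | 8.35 | 7.8 | 7.0 |
| Simulated group-by-time F-tests, two tests (%) | 9.8 | 9.6 | 9.3 | 8.8 | 7.8 | 7.1 |
| Simulated group and group-by-time, four tests (%) | 18.9 | 18.2 | 17.5 | 16.2 | 15.1 | 13.8 |

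Four independent tests would give 1 − 0.95⁴ = 18.5%.

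**3. Both scales required.** The false-positive rate is then at most 5%, so the inflation depends wholly on which rule is meant.

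**4. Room for a correction.** At 2.5% per scale the rate is 1 − 0.975² = 4.94% if independent, and never above 5%. At 40 per group and effect size 0.70, the noncentrality is 0.70 × √(40/2) = 3.130. The normal-approximation power is Φ(3.130 − 2.241) = 81.3%, and exact t gives 79.9%. One test at the full 5% has 87.1% (exact t). These powers are for the two-sample comparison, as in step 1, and not for the group-by-time F-test. Applying 0.70 to self-efficacy is an assumption.

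**The case against.** The strongest reply is that LATCH is already the implicit primary outcome. It alone drives the sample size, and a LATCH-only test keeps its 5%. A protocol that is not shown may name it outright. The point has weight and supports choosing LATCH in the fix. It does not settle the matter, because this SAP gives both scales the same role in measuring success and the same analysis.

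Three stronger readings are tempting, and the SAP does not support them.

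- **That the plan promises 5% overall and delivers 9-10%.** The 5% appears only as an input to the LATCH sample size. No overall error rate is claimed, no either-scale rule is stated, and the rate falls to about 7% if the scales are strongly correlated.
- **That the true rate is 14-19%.** This requires the group main effect to be read as a test of H1. That effect averages all three measurements, and the first was taken before any training. Group-by-time is the term that addresses a change due to training. The SAP lists both terms without choosing, so the higher figures show what follows if both are used. They do not describe a stated rule.
- **That the sample size points to the third meeting as the primary time point.** It refers only to scores after the application and names no visit. It supports LATCH, but not a particular visit or a different test.

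**Conclusion.** The concern holds in a conditional form. One hypothesis is measured by two scales of equal standing and tested identically on both, with no rule or correction across them, while the sample size rests on LATCH alone. Following the SAP as written leaves H0 open to rejection on either scale without error control.

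If either scale suffices, with one group-by-time test each at 5%, the false-positive chance is about 7-10% over correlations from 0.9 down to 0, and higher if the group main effect also counts. Confidence is high that the rule is missing. The percentage is only as firm as the assumed rule, level and correlation.

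**What to change.** State in the Statistical analysis section that H0 is decided by the LATCH group-by-time test at 5%, because LATCH is the basis of the sample size. Test self-efficacy at 5% only if LATCH is significant. This fixed sequence needs no more women and leaves the level for LATCH intact. The existing repeated-measures ANOVA can stay.

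If the two scales are meant to be co-equal, use Holm or 2.5% per scale instead. At 40 per arm, 2.5% per scale keeps about 80% power, on the assumption that effect size 0.70 also applies to self-efficacy.

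The change takes a few sentences, but it has two costs. Under the fixed sequence, a significant result on self-efficacy alone could no longer be claimed as support for H1. The SAP also reports in the past tense that the study was conducted in 2018 and that the data were normally distributed. The rule should therefore be dated and, if it was set after the data were seen, labelled post hoc. It would then clarify the report but could not restore prespecification.
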